There was no statistically significant effect of age (23-91 years), sex, body surface area (1.2 - 2.7 m²), or race on the clearance of ixazomib based on the results from a population PK analysis.

Further details on these studies are provided in the IB.

Clinical Trial Experience Using the Oral Formulation of Ixazomib: As of 27 March 2013, a total of 507 patients with differing malignancies (multiple myeloma, AL amyloidosis, nonhematologic cancers, and lymphoma) have been treated in studies evaluating the oral ixazomib formulation. These patients have been treated with different doses of ixazomib either as a single-agent treatment (in 201 patients) or in combination with currently clinically available treatments (in 306 patients). Information regarding the ongoing studies, patient populations, and doses investigated is included in Table 1-1.

Table 1-1 Clinical Studies of Oral Ixazomib

Trial/ Population	Description	Doses Investigated
C16003 RRMM N = 60	PO, TW, single agent	0.24-2.23 mg/m ² TW MTD: 2.0 mg/m ² DLT: rash, thrombocytopenia Closed to enrollment
C16004 RRMM N = 60	PO, W, single agent	0.24-3.95 mg/m ² W MTD: 2.97 mg/m ² DLT: rash, nausea, vomiting, diarrhea Closed to enrollment
C16005 NDMM N = 65	PO, W, combination with LenDex 28-day cycle	1.68-3.95 mg/m ² W MTD: 2.97 mg/m ² DLT: nausea, vomiting, diarrhea, syncope RP2D ^a : 4.0 mg fixed (switched to fixed dosing in phase 2, equivalent to 2.23mg/m ²) Closed to enrollment
C16006 NDMM N = 20	PO, TW (Arm A- 42 day cycle) and W (Arm B- 28 day cycle), combination with Melphalan and Prednisone	Arm A ^a : 3-3.7-mg fixed dose TW DLT: rash, thrombocytopenia, subileus Arm B ^a : 3-5.5-mg fixed dose, W DLT: Esophageal ulcer nausea, vomiting, hematemesis, thrombocytopenia, ileus, neurogenic bladder MTD = 3.0 mg
C16007 RRAL N = 27	PO, W, single agent	4-5.5-mg fixed dose ^a W DLT: thrombocytopenia, diarrhea, dyspnea, acute rise in creatinine, cardiac arrest MTD: 4.0 mg W
C16008 NDMM N = 64	PO, TW, combination with LenDex 21-day cycle	3.0-3.7-mg fixed dose ^a W MTD: 3.0 mg Closed to enrollment
C16009 Solid tumors, Lymphomas N = 54	PO, W, single agent	5.5-mg fixed dose ^a W
C16010	PO, W, with LenDex versus	4.0 mg W

Table 1-1 Clinical Studies of Oral Ixazomib

Trial/ Population	Description	Doses Investigated
RRMM N = 200	placebo-LenDex	
C16011 RRAL N = 4	PO, W, with Dex versus physician's choice of a Dex-based regimen	4.0 mg W
C16013 RRMM N = 9	PO, W, with LenDex	4.0 mg W
C16014 Symptomatic MM N=701	PO, combination with LenDex	ixazomib 4.0 mg or matching placebo on Days 1, 8, and 15, plus Len 25 mg on Days 1-21 (10 mg if low creatinine clearance, with escalation to 15 mg if tolerated) and Dex 40 mg (or 20 mg if >75 years old) on Days 1, 8, 15, and 22
C16015 Symptomatic MM with normal renal function or severe renal impairment N=28	PO, combination with Dex	Part A: ixazomib 3.0 mg on Day 1 Part B: ixazomib 4.0 mg on Days 1, 8, and 15, plus Dex 40 mg (or 20 mg if >75 years old) on Days 1, 8, 15 and 22 of a 28-day cycle
C16017 RR follicular lymphoma N=58	PO, W	4.0, 5.3, and 7.0 mg, W Treatment at RP2D once determined.
C16018 Advanced solid tumors or hematologic malignancies with varying degrees of liver dysfunction N=45	Part A: PO, Day 1 of 15-day cycle Part B: PO, W	1.5 mg (severe hepatic impairment), 2.3 mg (moderate hepatic impairment), or 4.0 mg (normal hepatic function)
TB-MC010034 RRMM N = 10	PO, W	4.0 mg, W Single agent: 4.0 mg Combination with Rd

Abbreviations: RRAL = Relapsed and/or refractory Primary systemic light chain (AL) amyloidosis; BSA = body surface area; Dex=dexamethasone; DLT = dose-limiting toxicity; IV = intravenously; LenDex = lenalidomide plus dexamethasone; MTD = maximum tolerated dose; NDMM = newly diagnosed multiple myeloma; PO = orally; RR= relapsed and/or refractory; RRAL= relapsed and/or

Table 1-1 Clinical Studies of Oral Ixazomib

Trial/ Population	Description	Doses Investigated
	refractory systemic light chain amyloidosis RRMM = relapsed and/or refractory multiple myeloma; TBD = to be determined; TW = twice weekly; W = weekly; RP2D= recommended phase 2 dose.	
	Note that blinded data from pivotal Studies C16010 and C16011 are not included.	
a	Approximate BSA and fixed dosing equivalence: 3 mg~ equivalent to 1.68 mg/m ² BSA dosing; 4.0 mg ~ equivalent to 2.23 mg/m ² BSA dosing; and 5.5 mg~ equivalent to 2.97 mg/m ² BSA dosing	

1.4 **Potential Risks of Ixazomib:**

The emerging safety profile indicates that ixazomib is generally well tolerated. The adverse events (AEs) are consistent with the class-based effects of proteasome inhibition and are similar to what has been previously reported with bortezomib, though the severity of some, for example peripheral neuropathy, is less. While some of these potential toxicities may be severe, they can be managed by clinical monitoring and standard medical intervention, or, as needed, dose modification or discontinuation. In the four ongoing studies (C16003, C16004, C16007, and C16009) investigating single-agent oral ixazomib in patients with differing malignancies (multiple myeloma, AL amyloidosis, non-hematologic cancers, and lymphoma), a total of 201 patients have been treated as of 27 March 2013. These patients have been treated with different doses of ixazomib, as they are all phase 1 trials. An overview of the most frequent (at least 10%) AEs occurring in the pooled safety population from single-agent oral ixazomib studies (C16003, C16004, C16007, and C16009) are shown in Table 1-2.

Table 1-2 Most Common (At Least 10% of Total) Treatment-Emergent Adverse Events in Oral Single-Agent Studies

Primary System Organ Class Preferred Term	Oral Single Agent Total n=201 (n%)
Subjects with at Least One Adverse Event	197 (98)
Gastrointestinal disorders	160 (80)
Nausea	106 (53)
Diarrhea	88 (44)
Vomiting	77 (38)
Constipation	46 (23)
Abdominal pain	33 (16)
General disorders and administration site conditions	151 (75)
Fatigue	103 (51)
Pyrexia	51 (25)
Edema peripheral	27 (13)

Table 1-2 Most Common (At Least 10% of Total) Treatment-Emergent Adverse Events in Oral Single-Agent Studies

Primary System Organ Class Preferred Term	Oral Single Agent Total n=201 (n%)
Asthenia	31 (15)
Nervous system disorders	92 (46)
Headache	29 (14)
Dizziness	26 (13)
Neuropathy peripheral	21 (10)
Metabolism and nutrition disorders	107 (53)
Decreased appetite	64 (32)
Dehydration	37 (18)
Blood and lymphatic system disorders	98 (49)
Thrombocytopenia	68 (34)
Anemia	42 (21)
Neutropenia	29 (14)
Lymphopenia	20 (10)
Skin and subcutaneous tissue disorders	90 (45)
Rash macular ^a	23 (11)
Musculoskeletal and connective tissue disorders	93 (46)
Back pain	24 (12)
Arthralgia	28 (14)
Respiratory, thoracic and mediastinal disorders	78 (39)
Cough	28 (14)
Dyspnea	30 (15)
Infections and infestations	89 (44)
Upper respiratory tract infection	31 (15)

Source: Ixazomib Investigator's Brochure Edition 7

Abbreviations: MedDRA = Medical Dictionary for Regulatory Activities, version 15.0.

Subject Incidence: A subject counts once for each preferred term. Percentages use the number of treated subjects as the denominator.

a Note that rash maculopapular and rash macular represent the two most common terms used to describe rash.

As of 27 March 2013, there are 5 studies that have completed enrollment or are actively enrolling patients with multiple myeloma to investigate oral ixazomib in combination with standard combination regimens. The most frequent (at least 10%) AEs occurring in the pooled safety population from Studies C16005, C16006, C16008, and C16013 are shown for all grades (Table 1-3). Note that in combination trials, “related” is defined as related to any study drug in the combination regimen.

Table 1-3 Most Common (At Least 10% of Total) Treatment-Emergent Adverse Events in Oral Combination Studies

Primary System Organ Class Preferred Term	Total Oral Combo Agent (5/6/8/13) n = 173 (n%)
Subjects with at Least One Adverse Event	163 (94)
Gastrointestinal disorders	139 (80)
Nausea	65 (38)
Diarrhea	81 (47)
Vomiting	51 (29)
Constipation	57 (33)
General disorders and administration site conditions	132 (76)
Fatigue	76 (44)
Pyrexia	39 (23)
Edema peripheral	61 (35)
Asthenia	20 (12)
Nervous system disorders	115 (66)
Headache	28 (16)
Dizziness	34 (20)
Neuropathy peripheral	45 (26)
Metabolism and nutrition disorders	91 (53)
Decreased appetite	25 (14)
Hypokalemia	34 (20)
Blood and lymphatic system disorders	88 (51)
Thrombocytopenia	49 (28)

Table 1-3 Most Common (At Least 10% of Total) Treatment-Emergent Adverse Events in Oral Combination Studies

Primary System Organ Class Preferred Term	Total Oral Combo Agent (5/6/8/13) n = 173 (n%)
Anemia	45 (26)
Neutropenia	43 (25)
Lymphopenia	20 (12)
Skin and subcutaneous tissue disorders	102 (59)
Rash maculopapular	29 (17)
Rash macular^a	22 (13)
Musculoskeletal and connective tissue disorders	99 (57)
Back pain	42 (24)
Pain in extremity	31 (18)
Arthralgia	22 (13)
Respiratory, thoracic and mediastinal disorders	80 (46)
Cough	36 (21)
Dyspnea	26 (15)
Infections and infestations	92 (53)
Upper respiratory tract infection	35 (20)
Psychiatric disorders	73 (42)
Insomnia	50 (29)

Source: Ixazomib Investigator's Brochure Edition 7

Abbreviations: MedDRA = Medical Dictionary for Regulatory Activities, version 15.0

Subject Incidence: A subject counts once for each preferred term. Percentages use the number of treated subjects as the denominator.

Data from ongoing blinded pivotal trials (C16010) are not included.

a Note that rash maculopapular and rash macular represent the two most common terms used to describe rash

The clinical experience with ixazomib also shows early signs of antitumor activity as evidenced by at least a 50% reduction in disease burden in some patients and prolonged disease stabilization in others across all ongoing trials. The antitumor activity has been

seen with single-agent ixazomib, when combined with established therapies, and across the malignancies studied (advanced solid tumors, non-Hodgkin's disease, Hodgkin's disease, relapsed and/or refractory multiple myeloma, relapsed or refractory systemic light chain amyloidosis, and newly diagnosed multiple myeloma) to date.(Kumar et al. 2014, Kumar et al. 2014, Kumar et al. 2014, Richardson et al. 2014)

Though additional data are needed to characterize the clinical benefit of this drug, the emerging data support the ongoing development of ixazomib.

Relapsed and/or Refractory Multiple Myeloma:

Please refer to the ixazomib IB for further information.

- 1.5** ***Pomalidomide:*** Pomalidomide, a thalidomide analogue, is an immunomodulatory agent that displays similar anti-angiogenic activity, but far greater anti-proliferative and immunomodulatory activity compared to the parent drug. Pomalidomide has also been shown to stimulate antibody-dependent cytotoxic T-cell activity (ADCC).

The efficacy of pomalidomide in relapsed myeloma has been shown in multiple trials.(Streetly et al. 2008, Lacy et al. 2009, Lacy et al. 2010, Lacy et al. 2011, San Miguel et al. 2013, Leleu et al. 2015) At tolerated doses (MTD=2 mg QD and 5 mg QOD), pomalidomide has been shown to be active in subjects with relapsed or refractory multiple myeloma (MM) (study CC-4047-00-001). In 45 subjects who received doses of pomalidomide ranging, by cohort, up to 10 mg daily, the most commonly occurring dose-limiting toxicity (DLT) was reversible neutropenia. As with other IMiDs administered to subjects receiving concomitant systemic steroids, deep vein thrombosis (DVT) was seen (in 1 subject each in this study and in its subsequent named patient supply rollover program).

Preliminary efficacy and safety data from a phase II study, led by Martha Lacy, et al, at Mayo Clinic, were published. Sixty patients with relapsed or refractory multiple myeloma were enrolled. Pomalidomide (CC-4047) was given orally at a dose of 2 mg daily on days 1-28 of a 28-day cycle and dexamethasone was given orally at a dose of 40 mg daily on days 1, 8, 15, 22 of each cycle. Patient also received aspirin 325 mg once daily for thromboprophylaxis. The study endpoints were the response rate in patients taking pomalidomide plus dexamethasone including patients with lenalidomide resistant refractory multiple myeloma, and safety of pomalidomide plus dexamethasone. Responses were recorded using the criteria of the International Myeloma Working Group. Thirty eight patients achieved objective response (63%) including CR in 3 patients (5%), VGPR in 17 patients (28%), and PR in 18 patients (30%). The CR + VGPR rate was 33%. Grade 3 or 4 hematologic toxicity occurred in 23 patients (38%); and consisted of anemia in three patients (5%), thrombocytopenia in two patients (3%) and neutropenia in 21 (35%). Among those that developed grade 3/4 neutropenia, all first experienced the neutropenia in cycle 1-3; no new patients experienced grade 3/4 neutropenia in cycle 4 or later. The most common non-hematological grade 3/4 toxicities were fatigue (17%) and pneumonia (8%). Other grade 3/4 non-hematological toxicities that occurred in less than 5% included diarrhea, constipation, hyperglycemia, and neuropathy. One patient (1.6%) had a thromboembolic event of deep vein thrombosis. Lacy et al. have also demonstrated promising clinical activity of pomalidomide in myeloma patients with persistent disease following lenalidomide treatment.

CC-4047-MM-002 is a Celgene sponsored phase 1b/2 multi-center, randomized, open-label, dose escalation study that is evaluating the safety and efficacy of oral

pomalidomide alone and in combination with low-dose dexamethasone in patients with relapsed and refractory multiple myeloma. Eligible patients must have received at least 2 prior regimens and all patients must have received prior treatment that includes lenalidomide and bortezomib. This study consists of a phase 1 single agent pomalidomide (maximum tolerated dose [MTD]) segment and phase 2 randomized (pomalidomide plus low-dose dexamethasone versus pomalidomide alone) segment. The MTD was 4 mg 21/28 days (there were 4 drug-related DLTs [Grade 4 neutropenia] at 5 mg). Neutropenia and anemia were the most common grade 3/4 toxicities; there was a dose-dependent increase in grade 4 neutropenia. Based on the preliminary safety and response data, 4 mg 21/28 days is the dose for the phase 2 segment.

Pre-clinical data and the prior experience with thalidomide and lenalidomide in the treatment of patients with myelofibrosis with myeloid metaplasia (MMM) provide the rationale for the use of pomalidomide in patients with MMM. This is further supported by the results of a Celgene sponsored trial (MMM-001) which indicated that pomalidomide therapy at 0.5 mg or 2 mg/day +/- an abbreviated course of prednisone is well tolerated in patients with myelofibrosis and active in the treatment of anemia.

- 1.6** ***Rationale for the current trial:*** Clearly patients with relapsed/refractory myeloma need newer therapies. The combination of pomalidomide and ixazomib provides a potentially powerful combination due to several reasons. Studies have not systematically studied the impact of induction therapy prior to salvage ASCT or the role of post-transplant consolidation and maintenance. While the responses to the salvage transplant is overall encouraging, it still remains rather short and approaches such as consolidation and maintenance that have improved outcomes in the setting of initial transplant should be evaluated in the context of salvage transplant. The combination of a proteasome inhibitor and an IMiD is one of the most effective treatment regimens in MM as has been seen with bortezomib or carfilzomib combinations with thalidomide or lenalidomide.⁶⁻⁸ A recently described mechanism of action of lenalidomide includes increased protein ubiquitination and brings into question mechanism of synergy between IMiDs and proteasome inhibitors. Despite this paradoxical preclinical data, clinical experience supports their synergistic activity.

Ixazomib is the first oral proteasome inhibitor to enter the clinic and has efficacy similar to bortezomib, with excellent activity seen in combination with lenalidomide in the setting of relapsed refractory MM in a recently reported phase 3 trial (TOURMALINE-MM1 study) (reference ASH abstract 2015 Moreau) . Pomalidomide is new IMiD with activity seen in nearly a third of the patients refractory to lenalidomide. The combination offers a convenient oral regimen that is also a potentially effective combination in patients with relapsed disease who would have been exposed to prior IMiDs and proteasome inhibitors. The oral proteasome inhibitor also offers the opportunity to study a convenient maintenance therapy in the setting of relapsed disease.

The current study proposes to examine the outcome following a salvage stem cell transplant, done following an effective induction therapy, and followed by consolidation and maintenance.

1.7 Potential Risks and Benefits of ixazomib

Please refer to the current ixazomib IB.

The clinical benefit of ixazomib continues to be studied in a comprehensive and global development plan that involves studies sponsored by Takeda. Ixazomib appears to show early signs of anti-tumor activity as evidenced by at least 50% reduction in disease

burden in some patients, including patients that have been heavily pretreated as well as those with newly diagnosed MM, and prolongs stabilization of the underlying disease in other patients across all ongoing trials. The preliminary findings are favorable when considering historical and currently available therapies for the patient populations evaluated. Though additional data are needed to characterize the clinical benefit of this drug, the emerging data support expanded development of ixazomib for the treatment of patients with advanced malignancy.

This study will be conducted in compliance with the protocol, good clinical practice (GCP), applicable regulatory requirements, and International Conference on Harmonisation (ICH) guidelines.

2.0 Goals

2.1 Primary

To estimate the rate of progression free survival at 18 months from study entry after therapy with Ixazomib (MLN9708) in combination with pomalidomide and dexamethasone followed by a single ASCT and consolidation with ixazomib in combination with pomalidomide and dexamethasone and maintenance with ixazomib in relapsed refractory ASCT naïve MM patients.

2.2 Secondary

- 2.21 To determine the best overall response rates (\geq PR) and deep responses (VGPR, CR, sCR) at various stages of treatment: after induction, after SCT, after consolidation and during maintenance.
- 2.22 To determine the overall survival from study entry.

2.3 Correlative Research

- 2.31 Assessment of minimal residual disease (MRD) by flow cytometry at various stages of treatment: after induction, day # 100 after SCT, after consolidation and during maintenance at year 1 and 2 from initiation of maintenance therapy
- 2.32 To determine the engraftment kinetics (WBC and platelet) following single salvage ASCT for relapsed disease

3.0 Patient Eligibility

3.1 Inclusion Criteria

- 3.11 Age ≥ 18 years.
- 3.12 Previously treated ASCT naïve MM patients, currently with relapsed or refractory disease who are being considered for single ASCT for relapsed disease. Patients must be eligible to undergo a stem cell transplant as per institutional criteria for selection at the time of registration.
- 3.13 The following laboratory values obtained ≤ 14 days prior to registration.
- Calculated creatinine clearance (using Cockcroft-Gault equation below)* ≥ 30 mL/min
 - Absolute neutrophil count (ANC) $\geq 1000/\text{mm}^3$
 - Platelet count $\geq 75 \times 10^9/\text{L}$ unless the participant has $\geq 50\%$ bone marrow infiltration in which case a platelet count of $\geq 50 \times 10^9/\text{L}$ is allowed
 - Hemoglobin ≥ 9.0 g/dL
 - Total bilirubin $\leq 1.5 \times$ the upper limit of the normal range (ULN) or if total bilirubin is $> 1.5 \times$ ULN, the direct bilirubin must be ≤ 2.0 mg/dL.
 - Alanine aminotransferase (ALT) and aspartate aminotransferase (AST) $\leq 3 \times$ ULN or $< 5 \times$ ULN if liver involvement

*Cockcroft-Gault Equation:

$$\text{Creatinine clearance for males} = \frac{(140 - \text{age})(\text{actual body weight in kg})}{(72)(\text{serum creatinine in mg/dL})}$$

$$\text{Creatinine clearance for females} = \frac{(140 - \text{age})(\text{actual body weight in kg})(0.85)}{(72)(\text{serum creatinine in mg/dL})}$$

- 3.14 Patients with measurable disease defined as at least one of the following:
- Serum monoclonal protein ≥ 1.0 g/dL by protein electrophoresis
 - ≥ 200 mg of monoclonal protein in the urine on 24-hour electrophoresis
 - Serum immunoglobulin free light chain ≥ 10 mg/dL AND abnormal serum immunoglobulin kappa to lambda free light chain ratio.
- 3.15 ECOG performance status (PS) 0, 1 or 2 ([Appendix I](#)).
- 3.16 Willing to provide informed written consent.
- 3.17 Negative pregnancy test done ≤ 7 days prior to registration, for persons of childbearing potential only.
- 3.18 Willing to follow strict birth control measures.
- Persons of childbearing potential, agree to one of the following:
- Practice 2 effective methods of contraception, at the same time, from the time of signing the informed consent form through 90 days after the last dose of study drug, AND must also adhere to the guidelines of any treatment-specific pregnancy prevention program, if applicable, OR
 - Agree to practice true abstinence when this is in line with the preferred and usual lifestyle of the subject. (Periodic abstinence [e.g., calendar, ovulation, symptothermal, post-ovulation methods] and withdrawal are not acceptable methods of contraception.)

Persons able to father a child: even if surgically sterilized (i.e., status post-vasectomy), must agree to one of the following:

- Agree to practice effective barrier contraception during the entire study treatment period and through 90 days after the last dose of study drug, OR
- Must also adhere to the guidelines of any treatment-specific pregnancy prevention program, if applicable, OR
- Agree to practice true abstinence when this is in line with the preferred and usual lifestyle of the subject. (Periodic abstinence [e.g., calendar, ovulation, symptothermal, post-ovulation methods] and withdrawal are not acceptable methods of contraception.)

- 3.19a Negative human immunodeficiency virus (HIV), hepatitis B and C test.
- 3.19b Willing to follow the requirements of the Pomalyst REMS program.
- 3.19c Willing to return to enrolling institution for follow-up (during the Active Monitoring Phase of the study).
- 3.19d Willing to provide bone marrow samples under IRB#521-93 for correlative research purposes (see Sections 6.2 and 14.0).

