The PK of ixazomib was similar with and without co-administration of clarithromycin, a strong CYP3A inhibitor, and hence no dose adjustment is necessary when ixazomib is administered with strong CYP3A inhibitors. Consistently, in a population PK analysis, co-administration of strong CYP1A2 inhibitors did not affect ixazomib clearance. Therefore, no dose adjustment is required for patients receiving strong inhibitors of CYP1A2. Based on information from the clinical rifampin DDI study, ixazomib C_{max} and AUC_{0-last} were reduced in the presence of rifampin by approximately 54% and 74%, respectively. Therefore, the co-administration of strong CYP3A inducers with ixazomib is not recommended.

Mild or moderate renal impairment ($CrCL \geq 30$ mL/min) did not alter the PK of ixazomib based on the results from a population PK analysis. As a result, no dose adjustment is required for patients with mild or moderate renal impairment. In a dedicated renal impairment study (C16015), unbound AUC_{0-last} was 38% higher in patients with severe renal impairment or ESRD patients requiring dialysis as compared to patients with normal renal function. Accordingly, a reduced starting dose of ixazomib is appropriate in patients with severe renal impairment or ESRD requiring dialysis. Pre- and post-dialyzer concentrations of ixazomib measured during the hemodialysis session were similar, suggesting that ixazomib is not readily dialyzable, consistent with its high plasma protein binding (99%).

The PK of ixazomib is similar in patients with normal hepatic function and in patients with mild hepatic impairment, as defined by the National Cancer Institute Organ Dysfunction Working Group (total bilirubin <1.5 times the upper limit of normal [ULN]), based on the results from a population PK analysis. Consequently, no dose adjustment is required for patients with mild hepatic impairment. In a dedicated PK study in patients with moderate (total bilirubin >1.5 to 3 times the ULN) or severe (total bilirubin >3 times the ULN) hepatic impairment (Study C16018), unbound dose-normalized AUC_{0-last} was 27% higher in patients with moderate or severe hepatic impairment as compared to patients with normal hepatic function. Therefore, a reduced starting dose of ixazomib is appropriate in patients with moderate or severe hepatic impairment.

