- Ixazomib is an anticancer drug. As with other potentially toxic compounds, caution should be exercised when handling ixazomib. It is recommended to wear gloves and protective garments during preparation when dispensed in clinic. Please refer to published guidelines regarding the proper handling and disposal of anticancer agents.
- 15.14 **Administration:** Ixazomib (MLN9708) capsules must be administered as intact capsules and are not intended to be opened or manipulated in any way. Capsules should be taken on an empty stomach with approximately 8 oz (1 cup) of water at least 1 hour before or at least 2 hours after food.
- Ixazomib should not be taken if the patient has had a serious allergic reaction to boron or boron containing products.
- 15.15 **Pharmacokinetic (PK) information:**

- a) Absorption: After oral dosing, ixazomib is rapidly absorbed with a median T_{max} of 1 hour. The lack of a discernible relationship between BSA and ixazomib clearance over a relatively wide BSA range (1.4-2.6 m²) indicates that total systemic exposure (AUC) following fixed dosing should be independent of the individual patient's BSA. A high-fat meal decreased both the rate and extent of absorption. Therefore, ixazomib should be administered on an empty stomach.
- b) Distribution: The steady state volume of distribution is large and is estimated to be 543 L. Ixazomib is 88-94% protein bound.
- c) Metabolism: Metabolism is the primary route for elimination of ixazomib by both CYP and non-CYP enzymes. CYP3A4 and 1A2 comprise the major CYP isozymes that contribute to ixazomib metabolism.
- d) Excretion: The mean terminal half-life is 9.5 days. Renal elimination is a minor clearance pathway for ixazomib. Dosing adjustment is not required in patients with mild and moderate renal impairment in studies. However, in a dedicated renal impairment study (C16015), unbound AUC_{0-last} was 38% higher in patients with severe renal impairment or end-stage renal disease (ESRD) requiring dialysis as compared to patients with normal renal function. Accordingly, a reduced starting dose of ixazomib is recommended in patients with severe renal impairment and ESRD requiring dialysis. Unbound systemic exposures of ixazomib are 27% higher in patients with moderate or severe hepatic impairment as compared to patients with normal hepatic function. A reduced starting dose of ixazomib is recommended for patients with moderate or severe hepatic impairment.

15.16 Potential Drug Interactions:

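### Section 3.13 admits patients with total bilirubin above 1.5 × ULN, for whom section 1.3 advises a reduced ixazomib start, but section 7.2 and Table 8.1 provide only a 4 mg start

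*Combined protocol and SAP*

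**What the plan says.** Section 3.13 offers two ways to meet the bilirubin criterion in the 14 days before registration: total bilirubin at or below 1.5 × ULN, or a higher total provided that "the direct bilirubin must be ≤ 2.0 mg/dL". The second route sets no ceiling on total bilirubin, and the exclusion criteria in 3.2 do not supply one.

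Section 1.3 (Pharmacokinetics and Drug Metabolism) grades hepatic impairment by total bilirubin. Below 1.5 × ULN is mild: "Consequently, no dose adjustment is required for patients with mild hepatic impairment". It then reports study C16018, done "in patients with moderate (total bilirubin >1.5 to 3 times the ULN) or severe (total bilirubin >3 times the ULN) hepatic impairment", where unbound dose-normalized AUC "was 27% higher in patients with moderate or severe hepatic impairment as compared to patients with normal hepatic function". It concludes: "Therefore, a reduced starting dose of ixazomib is appropriate in patients with moderate or severe hepatic impairment". Section 15.15 gives the same advice by category, with neither bilirubin values nor a dose: "A reduced starting dose of ixazomib is recommended for patients with moderate or severe hepatic impairment".

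Section 7.2 lists ixazomib 4 mg for induction, consolidation and maintenance, and its footnotes c and d allow a lower dose only after an earlier reduction. Table 8.1 has one starting dose, 4 mg. Its lower levels (3 mg, 2.3 mg, and 2.3 mg on Days 1 and 15 only) are tied to adverse events. No section states a hepatic starting dose.

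**The concern.** The eligibility rule lets in patients whom the background section classes as moderately or severely impaired, and the treatment schedule gives them the dose that the drug sections advise against. A site that follows 7.2 exactly has no instruction to do otherwise.

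The handling of parallel advice suggests an oversight. For kidney function, section 1.3 says "Accordingly, a reduced starting dose of ixazomib is appropriate in patients with severe renal impairment or ESRD requiring dialysis", and 3.13 removes that group by requiring "Calculated creatinine clearance (using Cockcroft-Gault equation below)* ≥ 30 mL/min". Section 1.3 also advises against strong CYP3A inducers, and 3.27 excludes recent users. The hepatic advice is carried into neither eligibility nor dosing.

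What is at stake is the starting exposure of an individual patient in a three-drug combination. The protections in the plan (weekly blood counts in cycles 1 to 3, omission of ixazomib for low counts, action on rash and neuropathy, the recovery rule in 8.11 and the stopping rule in 16.42) all act after the first dose.

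**Working it through.** The plan has no figure of its own on this point. The check compares the sections and then sizes the exposure difference.

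**Step 1: who passes 3.13.** The documents give no ULN for bilirubin, so assume 1.0 to 1.3 mg/dL.

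- Moderate band starts above 1.5 × ULN: 1.5 × 1.0 = 1.5 to 1.5 × 1.3 = 1.95 mg/dL.
- Severe band starts above 3 × ULN: 3 × 1.0 = 3.0 to 3 × 1.3 = 3.9 mg/dL.
- Total 2.2 with direct 2.0 mg/dL is 2.2/1.3 = 1.7 to 2.2/1.0 = 2.2 × ULN. That is moderate, mostly conjugated, and it passes.
- Total 4.0 with direct 2.0 mg/dL is 4.0/1.3 = 3.1 to 4.0/1.0 = 4.0 × ULN. That is severe, and it passes.

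Both bands therefore meet the bilirubin criterion. A direct bilirubin of 2.0 mg/dL alone exceeds 1.5 × ULN across this range, so the exception is not confined to unconjugated elevation.

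**Step 2: exposure by dose level.** The only input is the 27% in section 1.3, pooled over moderate and severe. It may overstate the effect just above 1.5 × ULN or in isolated unconjugated elevation, so ratios of 1.00 to 1.27 are shown. These are illustrative and do not bound either band. Equivalent dose = dose × ratio; percentage = equivalent dose / 4 mg.

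| Dose | Ratio 1.00 | Ratio 1.27 | % of intended 4 mg |
|---|---|---|---|
| 4 mg | 4.00 | 5.08 | 100 to 127 |
| 3 mg (level −1) | 3.00 | 3.81 | 75 to 95 |
| 2.3 mg (level −2) | 2.30 | 2.92 | 58 to 73 |

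**Step 3: nearest existing level.** The dose matching 4 mg at the full 27% is 4/1.27 = 3.15 mg, so 3 mg is nearest. A 3 mg start would exceed the intended exposure only if the ratio were above 4/3 = 1.33. Table 1-1 shows that C16018 gave 2.3 mg in moderate and 1.5 mg in severe impairment; it lists 4.0 mg for normal hepatic function only.

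**Step 4: against a known MTD.** Table 1-1 gives 2.97 mg/m² weekly with lenalidomide and dexamethasone (C16005), which its footnote a equates to about 5.5 mg. 5.08/5.5 = 92%, so the upper figure stays below that MTD; passing it needs a ratio above 5.5/4 = 1.375. The documents give no MTD for ixazomib with pomalidomide.

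**Step 5: the statistical design.** For the rule of at least 14 successes in 21, the exact binomial tail is 0.0946 at a success proportion of 0.50 and 0.8701 at 0.75. These reproduce the 0.095 and 0.870 in section 16.24. Nothing here alters them.

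**The case against.** The strongest reply is that the gap may be empty in practice. Candidates must meet institutional transplant criteria (3.12), the ALT/AST limits (3.13) and negative hepatitis tests (3.19a). They must be free of serious co-morbidity or uncontrolled illness (3.23, 3.28), recovered from prior chemotherapy (3.29e) and without AL amyloidosis (3.29g). The exception may be meant for benign unconjugated elevation, where 27% could be too high. The advice is printed in 15.15, dosing is supervised (7.4), and the Investigator's Brochure, to which 1.3 and 15.17 refer, may say more. The study plans only 25 patients.

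The point about reach stands: the affected group is small and may be nil. The rest does not close the gap. Those criteria may exclude a patient but give no dose to one who is enrolled. The protocol does not limit the exception to unconjugated elevation, and section 1.3 grades by total bilirubin. Section 7.2 does not refer to 15.15, and 15.15 names no level.

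A reader might infer more than the documents support:

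- That 15.15 itself sets bilirubin limits. It does not; the bands are in 1.3 only.
- That the instruction in 8.0 to follow the table strictly for two cycles compels a 4 mg start. It governs adverse-event modifications only.
- That sites would dose the same patient differently. This is speculative: the schedule prints a single dose, and 10.8 treats a multisite study as a contingency.

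**Conclusion.** The conflict is in the text and should be fixed. Section 3.13 admits patients whom section 1.3 would start on less ixazomib, and 7.2 with Table 8.1 gives them 4 mg. Confidence is high for the mismatch and does not extend to any consequence.

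On the one figure available, the starting exposure would be 100% to 127% of that intended. This assumes that the pooled 27% applies and that exposure is proportional to dose, as section 1.3 reports. How many patients qualify, and whether any would pass transplant selection, cannot be told from the documents.

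A reader might infer that patients would be harmed or dosed above a tolerated level. The documents do not show this: the upper figure is below the one comparable MTD, although none is given with pomalidomide. Nor does the point touch the sample size, the error rates or the 18-month endpoint.

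**What to change.** 1. In 3.13, cap the exception at total bilirubin of 3 × ULN. Table 8.1 has no level as low as the 1.5 mg that C16018 used in severe impairment.
2. In 7.2 and Table 8.1, add that patients registered with total bilirubin above 1.5 and up to 3 × ULN start ixazomib at level −1 (3 mg). Ask the drug supplier to confirm this level, because no document tests 3 mg in this group and C16018 used 2.3 mg.
3. Recheck bilirubin before consolidation and before maintenance. Keep 3 mg while it remains above 1.5 × ULN; otherwise apply footnotes c and d. Without such a sentence those footnotes do not clearly cover a lower start that was not a reduction for toxicity. A 3 mg dose fixed for the whole study might also be inferred, but it would ignore bilirubin that returns to normal.

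An alternative is to restrict the exception to isolated unconjugated elevation with direct bilirubin in the normal range, keeping 4 mg only if the supplier confirms it.

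The cost is one criterion and a few sentences of dosing text. No new test is needed, because 4.1 already collects total and direct bilirubin at baseline and each cycle. A few candidates may become ineligible. A patient whose exposure is truly normal would receive 3/4 = 75% of the intended dose. A 3 mg start also leaves two reductions before discontinuation in Table 8.1 instead of three.
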